### Open-label extension epoch

The purpose of this open-label period is to observe the additional vascular effects of sacubitril/valsartan that occur beyond 12 weeks of treatment.

After 12 weeks of successful double-blind, active treatment, patients will continue into the 12 week open-label extension epoch. Patients will have received the final dose of double-blind treatment medication in the clinic at Week 12 (Visit 6).

- ALL patients will need to have a 36-hour washout from study treatment prior to starting the open-label extension to ensure that the blinding of the core study is maintained and to reduce the risk of angioedema.
- To facilitate this washout, patients will be instructed NOT to start their open-label treatment until the evening of the following day.
- All patients will start open-label treatment on sacubitril/valsartan 49/51 mg BID (Dose level 2), unless they completed the double-blind treatment epoch on Dose Level 1. Instead, these patients will enter the open-label epoch on sacubitril/valsartan 24/26 mg BID dose (Dose level 1).
- Study treatment will be force-titrated every 2 weeks to reach the target dose of sacubitril/valsartan 97/103 mg BID (Dose Level 3).

Deviation from the titration schedule or dose adjustments will only be allowed if indicated per protocol defined safety and tolerability criteria (See [Section 5.5.5](#), [Table 5-7](#)), and investigator judgement, if the investigator believes that adjustment/elimination of concomitant medications is not possible or does not alleviate the side effects of concern.

Follow-up safety visits will occur throughout the study at Weeks 1, 2, 4, 12, 14 and 24 (Visits 3, 4, 5, 6, 7, and 8).

Primary efficacy assessments will be conducted at Screening/Baseline, Day 1 (Visit 2) pre-randomization, and Week 12 (Visit 6).

[figure not shown]
Patients will be contacted by phone at approximately 30 days following the last administration of study treatment at Week 24 (Visit 8), or early withdrawal, in order to determine if any SAE(s) occurred during this time period. These SAEs will be recorded in the source document only and must be reported to Novartis. Attempts to contact the patient should also be recorded in the source document.

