Every SAE occurring after the patient has provided informed consent and until 30 days following the last administration of study treatment must be reported directly to the Novartis Drug Safety and Epidemiology Department within 24 hours of learning of its occurrence.

No interim analysis is planned. If it is deemed necessary for internal decision making, due to patient safety, an interim analysis will be conducted by an independent statistical group.

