### **5.6.2 Discontinuation of study treatment**

Discontinuation of study treatment for a patient occurs when study drug is stopped earlier than the protocol planned duration, and can be initiated by either the patient or the investigator.

The investigator must discontinue study treatment for a given patient if, on balance, he/she believes that continuation would negatively impact the risk/benefit of trial participation.

Patients may voluntarily discontinue the study drug for any reason at any time.

Study treatment must be discontinued under the following circumstances:

- Patient wish
- Withdrawal of consent
- Pregnancy (see [Section 6.5.8](#) and [Section 7.6](#))
- Use of prohibited treatment as per recommendations in [Table 5-9](#)
- Any protocol deviation that constitutes a risk to the patient

- Any situation in which study participation might result in a safety risk to the patient
- Unresolved worsening HF

Study medication may be discontinued at the investigator's discretion if any of the following serious suspected drug-related AEs occur:

- Symptomatic hypotension
- Suspected occurrence of angioedema. A patient with any signs or symptoms of clinically significant angioedema should be thoroughly evaluated by the investigator to determine if it constitutes a reason for discontinuation of study medication.
- Any laboratory abnormalities that in the judgment of the investigator, taking into consideration the subject's overall status, prevents the subject from continuing participation in the study.

Depending on the serum potassium, blood pressure, or eGFR, patients may need to have their study drug dose or the dose of another concomitant medication reduced or discontinued; or, if appropriate, have potentially contributing agents adjusted. Refer to appendices for treatment guidelines for hyperkalemia, hypotension or renal dysfunction, respectively.

If discontinuation of study treatment occurs, the patient should NOT be considered withdrawn from the study. The investigator must determine the primary reason for the patient's premature discontinuation of study treatment and record this information on End of Study Treatment eCRF. After study treatment discontinuation, the patient should attend the regularly scheduled visits and have all study assessments performed.

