## **6 Visit schedule and assessments**

[Table 6-1](#) lists all of the assessments and indicates with an "X" when the visits are performed. Assessments that will only be reported in the source documentation are marked with an 'S'.

Patients must be seen for all visits on the designated day, or as close to it as possible, including those on dose interruptions or discontinued treatment. A visit window of +/- 3 days is allowed. Every effort should be made to respect the time frame for the primary efficacy endpoint at Week 12 (Visit 6) visit.

Missed or rescheduled visits should not lead to automatic discontinuation. Patients who prematurely discontinue the study for any reason should be scheduled for a visit as soon as possible, at which time all of the assessments listed for Visit 6 (End of Treatment) or Visit 8 (End of Study) will be performed, depending on the epoch from which the patient prematurely discontinues from the study. See [Section 5.6.3](#). At this final visit, all dispensed investigational product should be reconciled and the adverse event and concomitant medications reconciled on the eCRF.

[figure not shown]
Patients will be contacted by phone at approximately 30 days following the last administration of study treatment, Week 24 (Visit 8), or early study discontinuation, in order to determine if any SAE(s) occurred during this time period. These SAE(s) will be recorded in the source document only and must be reported to Novartis. Attempts to contact the patient should be recorded within the source document.

Every SAE occurring after the patient has provided informed consent and until 30 days following the last administration of study treatment must be reported directly to the Novartis Drug Safety and Epidemiology Department within 24 hours of learning of its occurrence.

Unscheduled visits for safety/medication evaluation/unscheduled assessments are permitted at any time during the study.

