### **7.2.2 SAE reporting**

To ensure patient safety, every SAE, regardless of causality, occurring after the patient has provided informed consent and until 30 days [after the last study visit/ following the last administration of study treatment if there are post-treatment follow-up visits with no required procedures] (*please select as appropriate, see comment below*) must be reported to Novartis within 24 hours of learning of its occurrence. Any SAEs experienced after the 30-day period [after the last study visit/ following the last administration of study treatment if there are post-treatment follow-up visits with no required procedures] should only be reported to Novartis if the investigator suspects a causal relationship to study treatment.

All follow-up information for the SAE including information on complications, progression of the initial SAE and recurrent episodes must be reported as follow-up to the original episode within 24 hours of the investigator receiving the follow-up information. An SAE occurring at a different time interval or otherwise considered completely unrelated to a previously reported one must be reported separately as a new event.

Information about all SAEs is collected and recorded on the Serious Adverse Event Report Form; all applicable sections of the form must be completed in order to provide a clinically thorough report. The investigator must assess the relationship of each SAE to *each specific component of study treatment (if study treatment consists of several components)* complete the SAE Report Form in English, and submit the completed within 24 hours to Novartis. Detailed instructions regarding the submission process and requirements for signature are to be found in the investigator folder provided to each site.

Follow-up information is submitted as instructed in the investigator folder. Each re-occurrence, complication, or progression of the original event must be reported as a follow-up to that event regardless of when it occurs. The follow-up information should describe whether the event has resolved or continues, if and how it was treated, whether the blind was broken or not, and whether the patient continued or withdrew from study participation.

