The study day will be calculated as the difference between the date of assessment and the date of randomization plus 1. If the date of assessment is prior to the date of randomization, the study day will be negative and will be calculated as the difference between the date of the assessment and the date of randomization.

Double-blind phase

Assessments performed at Weeks 1, 2, 4, or 12 (including, but not limited to, vital signs) will be assigned to the double-blind phase for summarization purposes. Unscheduled assessments are not assigned to a study phase for purposes of by-visit summaries.

For summarization of adverse events [AEs], medications, protocol deviations, notable vital signs and laboratory abnormalities, angioedema, and hospitalizations/ED visits/unplanned outpatient clinic visits due to worsening HF symptoms by study phase, an assessment during the double-blind phase is defined as any assessment obtained in the following time interval:

Date of randomization (or date of first administration of study treatment, as appropriate) through the date of the Week 12 visit, inclusive. For patients without a Week 12 visit, a projected Week 12 visit date will be derived relative to their randomization date.

Open-label phase

Assessments performed at Weeks 14 or 24 (including, but not limited to, vital signs) are assigned to the open-label phase for summarization purposes. Unscheduled assessments are not assigned to a study phase for purposes of by-visit summaries.

For summarization of AEs, medications, protocol deviations, notable vital signs and laboratory abnormalities, angioedema, and hospitalizations/ED visits/unplanned outpatient clinic visits due to worsening HF symptoms by study phase, an assessment during the open-label phase is defined as any assessment obtained in the following time interval:

After the date of the Week 12 visit. For patients without a Week 12 visit, a projected Week 12 visit date will be derived relative to their randomization date.

Patients who died, withdrew consent, or were lost to follow-up prior to or on their projected Week 12 visit date will be excluded from the open-label phase.

Last contact

The date of last contact will be determined as the later of the following dates:

- The last visit date for each patient derived by examining all visit data collected in the eCRFs
- Date of discontinuation/study phase completion for the double-blind and open-label phases

Year, month and week

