2.8.1.2 General rules for AE reporting

AE summaries will include all treatment-emergent AEs (TEAEs). TEAEs are defined as AEs starting on or after the first day of study treatment. All AEs will be listed. AEs starting prior to the first day of study treatment (non-TEAEs) will be flagged in the listings.

All TEAEs will be summarized by study phase as defined in Section 2.1.1.

TEAEs will be summarized by presenting the number and percentage of patients having at least one TEAE, having at least one TEAE in each primary SOC, and for each PT using MedDRA terminology. A patient with multiple occurrences of a TEAE will be counted only once in the AE category.

Separate summaries will be presented by SOC, PT and severity. A patient with multiple severities for an AE will be summarized under the worse severity recorded for the event.

Any information collected will be listed as appropriate.

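### SAEs learned of at the 30-day call reach the sponsor's safety database but have no stated route into the clinical database behind the SAP's SAE tables

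*Protocol*

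**What the plan says.** **Recording rule.** Patients are telephoned about 30 days after the last dose at Week 24, "or early withdrawal, in order to determine if any SAE(s) occurred during this time period" (Protocol 3.1). The next sentence sets the destination: "These SAEs will be recorded in the source document only and must be reported to Novartis". Section 5.6.1 has the same rule, and Section 6 repeats it almost word for word: "These SAE(s) will be recorded in the source document only and must be reported to Novartis". Table 6-1 footnote 18 also directs the call to source. At scheduled visits, by contrast, the AE/SAE row of Table 6-1 is coded D, meaning the clinical database.

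**Reporting window.** Section 3.1 requires that every SAE from consent "until 30 days following the last administration of study treatment must be reported directly to the Novartis Drug Safety and Epidemiology Department". Sections 5.6.1 and 6 and footnote 18 also use 30 days after the last dose. Section 7.2.2 instead leaves two alternatives in brackets, one counted from the last visit and one from the last dose, with the author prompt "please select as appropriate, see comment below".

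**SAP.** Section 2.8.1.2: "TEAEs are defined as AEs starting on or after the first day of study treatment". No upper limit is given. Section 2.1.1 runs the double-blind phase to the Week 12 visit, and adds: "For patients without a Week 12 visit, a projected Week 12 visit date will be derived relative to their randomization date". Sections 2.8.1.3 and 2.8.2 list the SAE and death summaries without naming a data source or cut-off.

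**The concern.** The protocol collects SAEs for 30 days after the last dose, and the SAP's definition would count them. Between the two, the recording rule stops these events at the source document and the sponsor's safety report. Followed as written, an SAE first learned of at the call is known to the sponsor and absent from the SAP's SAE tables.

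For a patient who completes Week 24, the omission affects only the single-drug open-label summary. For a patient who leaves the study during the randomized epoch, the call is the only scheduled contact after the final visit, and the days it covers lie largely or wholly inside what the SAP labels double-blind. Those events belong in the arm-by-arm SAE table. If the arms lost patients at different rates, the omission would differ by arm. The documents do not say that they will.

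**Working it through.** The plan gives no figure for this point, so there is none to reproduce. The check traces where an event goes, then bounds the scale.

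**Route of an SAE first learned of at the call**
1. Recorded in source only (Protocol 3.1, 5.6.1, 6; footnote 18).
2. Reported to the sponsor within 24 hours on the SAE Report Form (Section 7.2.2).
3. Transfer or reconciliation between safety reports and the analysis database: none described in Protocol Section 8.3 or in the SAP.
4. Would the SAP count it? Yes. It starts after the first dose, and there is no end limit (SAP 2.8.1.2).

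The chain breaks at step 3.

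**Who is affected**
- *Stopped drug but still in the study:* not by this route while they attend. Section 5.6.2 says: "After study treatment discontinuation, the patient should attend the regularly scheduled visits and have all study assessments performed". AEs and SAEs are collected at visits or by telephone.
- *Withdrew consent:* Section 5.6.3 generally bars further contact, so usually there is no call.
- *Left the study before Week 12 and still contactable:* affected, within the randomized comparison.
- *Completed Week 24:* affected, open-label only. The call covers 30 of 168 + 30 = 198 days, or 15%.

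**Share of the window that rests on the call.** Assume the patient leaves the study and takes the last dose on day d. The share is 30/(d + 30). The days inside the projected double-blind phase, which ends at day 84, are min(30, 84 − d).

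| d | Share | Days in projected double-blind phase |
|---|---|---|
| 14 | 30/44 = 68% | 30 |
| 28 | 30/58 = 52% | 30 |
| 42 | 30/72 = 42% | 30 |
| 56 | 30/86 = 35% | 28 |

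**Ceiling.** Protocol 9.8 allows 20% dropout: 0.20 × 432 = 86.4, about 86 patients. Then 86 × 30 = 2,580 patient-days, against 432 × 84 = 36,288 planned double-blind days, or 7.1%.

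**Illustrative counts.** The documents give no SAE rate. Assume a 30-day SAE risk of 2% to 10% and 22 to 86 early study leavers:
- Low end: 0.02 × 22 = 0.4 patients with an SAE outside the tables.
- High end: 0.10 × 86 = 8.6 patients.
- Open-label: Table 5-3 expects about 346 entrants. If all complete, 346 × 0.02 = 6.9 to 346 × 0.10 = 34.6 patients. None of these enters the randomized comparison.

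**The case against.** **The events are not lost.** They go to the sponsor within 24 hours on a dedicated form. This is correct. A reader might infer from the source-only wording that the sponsor never sees these SAEs, and the same sentence rules that out. The gap lies between the safety database and the analysis database.

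**The AE period ends at the end of study visit (Protocol 7.1), so the SAP's open-ended definition works only on data collected to that point, and the projected Week 12 date merely labels recorded events.** This explains how the mismatch arose but does not remove it. The protocol itself collects SAEs to 30 days after the last dose, and the SAP neither excludes them nor provides for merging them.

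**The unselected text in Section 7.2.2 does not cause an undercount.** Correct. It governs reporting to the sponsor, and four other places agree on last dose. A patient who stops drug at Week 4 but keeps attending has SAEs entered in the database to Week 24 under either window.

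**Deaths are captured elsewhere.** Largely correct. Protocol 7.1 collects deaths on the Study Completion CRF, and SAP 2.3.1 lists death as a disposition in both phases. No text keeps a death learned of at the call off that form. A reader might infer that death tables will be short, but the documents leave this possible and do not show it.

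**Safety is descriptive and differential dropout is speculative.** Both are true, and they limit the consequence. An incomplete descriptive SAE table is still worth avoiding when the sponsor already holds the events.

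**Conclusion.** The point holds as a data-flow gap. SAEs first learned of at the 30-day call are reported to the sponsor but, by stated rule, are recorded in source only. They have no stated route into the SAP's SAE tables, whose definition would include them. Most such calls concern open-label completers. The part that touches the randomized comparison is limited to patients who leave before Week 12 and can still be contacted.

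The number affected is unknown. The 86 patients and the 7.1% of patient-days are a loose ceiling: 20% is a sample-size allowance, patients who only stop drug remain under database collection, and those who withdraw consent are mostly not called. They should not be read as an estimated SAE undercount. The range of 0.4 to 8.6 patients rests wholly on assumed risks and assumed numbers of leavers. The primary efficacy analysis is not affected.

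Section 7.2.2 is a separate drafting inconsistency in sponsor reporting.

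**What to change.** 1. In Protocol 3.1, 5.6.1, 6 and Table 6-1 footnote 18, replace source-only recording with entry of call-detected SAEs, and any deaths, in the AE/SAE eCRF. Alternatively, require documented reconciliation of the safety and clinical databases before lock.
2. In SAP 2.8.1.2 to 2.8.2, name the data source and state the cut-off for the SAE and death tables. If events after the last visit are meant to be excluded, say so.
3. In Protocol 7.2.2, remove the prompt and the brackets and give one window consistent with Sections 3.1, 5.6.1, 6 and footnote 18. A longer window, such as the later of last dose and last visit, would be a preference. The documents do not require it.

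Cost: a few extra eCRF entries for events the sponsor already receives, or some reconciliation work before lock, plus wording changes.

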**Figure 3-1 Study design**

### 3.2 Rationale for study design

The Evaluate-HF study is designed to provide a definitive assessment of the hemodynamic mechanism of action of sacubitril/valsartan in HFrEF.

In the CHOIR study, ACE/NEP inhibition with omapatrilat was associated with greater reductions in pulse pressure and Zc than enalapril after 12 weeks of treatment. Based on this, the double-blind treatment epoch of this study was designed to be 12 weeks. Additionally, given the superior results obtained with sacubitril/valsartan in the PARADIGM-HF trial, the duration of the double-blind period also limits the patients' exposure to the current standard of care, enalapril.

Prior to the double-blind treatment epoch, we wanted to ensure that patients had the opportunity to be optimized on treatment with guideline-directed therapy for HFrEF, other than ACEi and ARBs. As many patients are able to be up-titrated on medications in a 4 to 6 week period, we have allowed up to 6 weeks for the screening epoch.

We wanted the ability to assess the vascular effects of patients who switch from enalapril to sacubitril/valsartan as well as to understand if there are additional vascular effects in patients who have extended treatment with sacubitril/valsartan. We believe that 12 weeks of open-label treatment was enough time to evaluate both of these measures.

### 3.3 Rationale for dose/regimen, route of administration and duration of treatment

Sacubitril/valsartan 97/103 mg BID was selected as the target dose because it was the dose used in the PARADIGM-HF study where it was shown to have superior results versus enalapril in reducing CV death and heart failure hospitalizations. This is also the USPI approved target dose.

In addition, this dose delivers similar exposures of valsartan as Diovan 160 mg BID, the maximal approved Diovan dose for heart failure and the dose recommended in international guidelines for the treatment of heart failure and biomarker analysis (increase in ANP and cGMP) indicates that this sacubitril dose delivers approximately 90% of its maximal neutral endopeptidase (NEP) inhibition. Dosing with 97/103 mg twice daily ensures sustained NEP inhibition over 24 hours, which is thought to be critical for patients with heart failure.

### **3.4 Rationale for choice of comparator**

Treatment with ACEi has been well established as the standard of care for RAAS blockade and is recommended by treatment guidelines as a 1A recommendation for all patients with CHF and reduced LVEF, unless ACEi-intolerant. Additionally, ACEi may reduce aortic stiffness by opposing vasoconstrictive, hypertrophic, and profibrotic effects of angiotensin II on the vessel wall.

As a well-studied ACEi in heart failure, enalapril has been selected as the comparator for this study with a target dose of 10 mg BID. The 10 mg BID dose was the same target dosage studied in the SOLVD study and is the dose that was chosen in the PARADIGM-HF trial. The same dose will be used in this study so that we can appropriately assess the hemodynamic benefits of the drug and whether it supports the clinical outcomes that were seen in both trials.

